### **3.1 Database closure agreement**

Once the database is closed for the analysis, if abnormal and/or inconsistent values are detected in a results table, the database shall not be re-opened for modification, but the abnormal datum and the way in which it was processed will be informed and agreed with the sponsor (such as by assignment of missing datum or elimination of the case, depending on the statistical method to be used in the analysis in question). Missing data shall not count and shall be considered as missing.

Any change to said table will be described in writing in the report, as shall the procedure applied (such as assignment of missing datum, interpolation, elimination of the case, etc.).

For the final statistical analysis, the database shall be re-opened and the study data and affected tables will be changed only if a change in the contractual conditions is considered with the sponsor.

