## **9.7 DATA ANALYSIS**

Analyses will be performed by Boehringer Ingelheim's designees. The analysis population will consist of all eligible patients (i.e. all patients fulfilling all inclusion criteria and no exclusion criteria).

In this non-interventional study, cross-sectional data at study visit will be collected for non-valvular AF patients with a VKA or DOAC therapy. Once the study has been completed and all data from the last patient have been recorded, the database will be closed and statistical analysis will be performed.

The proposed methods for statistical analysis presented below are a summary of the methods that will be applied in the study to analyze the data collected and to answer the study objectives. Missing data will not be imputed and will be left as lost.

Summary statistics for continuous variables will include the N, mean, standard deviation, minimum, Q1 (lower quartile), median, Q2 (upper quartile), and maximum value; tabulations of categorical variables will present all possible categories and will display the number of observations per category as well as percentages. Estimates will be presented with 95% confidence intervals for the variables of interest. Additional details of the planned analysis will be provided in the statistical analysis plan (SAP).

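### SAP 3.1 allows undefined abnormal values seen in results tables after database closure to be set missing, interpolated or removed with the patient, by agreement with the sponsor

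*SAP*

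**What the plan says.** SAP 3.1 (Database closure agreement) covers the period after the database is closed. It says that "if abnormal and/or inconsistent values are detected in a results table, the database shall not be re-opened for modification". Instead, "the abnormal datum and the way in which it was processed will be informed and agreed with the sponsor". The examples given at that point are setting the value to missing and eliminating the case, the choice "depending on the statistical method to be used in the analysis in question".

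The next paragraph requires disclosure: "Any change to said table will be described in writing in the report", together with the procedure used, "such as assignment of missing datum, interpolation, elimination of the case, etc". This list adds interpolation and is open-ended. The section also says that missing data stay missing, and it ties any re-opening of the database to a change in the contractual conditions.

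Other relevant text:
- Protocol 9.7 states "Missing data will not be imputed and will be left as lost" and defines the analysis population as all eligible patients. SAP 4 likewise bases the analyses on eligible patients.
- SAP 8.1 produces the primary quality-of-life tables for the controlled, uncontrolled and total populations.
- Protocol 9.6 and 9.8 describe eCRF edit checks for missing, out-of-range, illogical or possibly wrong entries.

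**The concern.** A data-handling rule protects the results only if it is fixed before they are seen. Here the trigger is something noticed in a results table, the terms that would limit it are undefined, and the remedy is chosen afterwards. The primary tables show the two groups side by side, so whoever notices a value there can also see which way a change would move a group estimate.

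The study is descriptive, so no type I error rate is at stake. The group summaries of the Sawicki items and dimensions are the main product of the study, however, and this clause can alter them. Two of the named remedies also depart from rules stated elsewhere in the plan.

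**Working it through.** The plan gives no figure on this point, so the check is mainly a comparison of texts, followed by an illustration of size.

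**1. What limits the choice?**
- Definition of abnormal or inconsistent: none in either document.
- Remedy fixed for each type of problem: none, only the pointer to the statistical method.
- Reviewer masked to group: not required.
- Result from the unmodified data shown as well: not required.
- Written description of the change in the report: required.

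**2. Do the remedies fit the rest of the plan?**
- *Set to missing.* This fits the rule that missing data stay missing, provided the reason for blanking a value is fixed in advance.
- *Interpolation.* This puts an estimated value in place of a recorded one. It conflicts with the no-imputation rule in protocol 9.7. It also has little meaning here, because each patient has one visit and so no neighbouring time points.
- *Elimination of the case.* Protocol 9.7 and SAP 4 analyse every patient who meets the inclusion criteria and no exclusion criterion. An odd value is not an exclusion criterion. Removal fits only if the patient then fails an eligibility check listed in SAP 4.

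**3. A consequence for group membership.** SAP 4 requires a completed TTR for a VKA patient to be eligible. SAP 5.1 assigns VKA patients below the TTR cut-off to the uncontrolled group and everyone else to the controlled group. If a VKA patient's TTR is set to missing after closure, SAP 4 makes the patient ineligible, while SAP 5.1 read literally leaves the patient among those assigned to the controlled group. The SAP does not say which applies.

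**4. Illustration of size.**

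Inputs from the documents: uncontrolled group n = 170 (protocol 9.5) and item scale 1 to 6 (SAP 8.1). Assumptions not in the documents: group mean m of 2 to 3 and SD of 1.0 to 1.5.

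The fall in the mean when k patients scoring 6 are removed is k(6 − m)/(n − k).

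| k | m = 3 | m = 2 |
|---|---|---|
| 1 | 3/169 = 0.018 | 4/169 = 0.024 |
| 5 | 15/165 = 0.091 | 20/165 = 0.121 |
| 9 | 27/161 = 0.168 | 36/161 = 0.224 |

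The 95% CI half-width is 1.96 × SD/√170. For SD 1.0 this is 1.96/13.04 = 0.150, and for SD 1.5 it is 2.94/13.04 = 0.225.

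Five removals therefore amount to between 0.091/0.225 = 40% and 0.121/0.150 = 81% of the half-width. One removal amounts to between 0.018/0.225 = 8% and 0.024/0.150 = 16%.

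**The case against.** The strongest reply is that the clause is about data errors. The protocol's related wording on edit checks points to out-of-range or illogical entries, and those checks should make such values rare by closure. A data management plan, not available here, may add further cleaning rules. The closed data stay unaltered, every change must be described, and no hypothesis test is affected. Interpolation appears only in the sentence on what the report must describe; the operative sentence names setting to missing and elimination.

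Much of this stands and limits the weight of the point. It does not remove it. Disclosure tells the reader that a choice was made but does not fix it beforehand. Edit checks do not define abnormal for the purpose of SAP 3.1. A procedure listed for reporting is one the SAP contemplates using.

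A reader might infer more than the documents support:
- *That the groups are defined by the sponsor's drug class.* They are defined by anticoagulation control. VKA patients fall in either group according to TTR, and the controlled group pools well-controlled VKA patients with all DOAC patients.
- *That the results could not be reproduced from the closed data.* The database is not re-opened and changes are reported, so a specific enough description would allow reconstruction.
- *That the SAP says valid scores of 6 may be removed.* It does not. The wording is loose enough not to exclude this, but 6 is a printed response option.

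**Conclusion.** The point holds as a defect in the stated rule. SAP 3.1 permits changes to primary estimates that are prompted by results tables, agreed with the sponsor and not prespecified. Interpolation conflicts with protocol 9.7, and discretionary removal of patients conflicts with analysing all eligible patients. No misuse is shown or alleged.

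The size cannot be determined from the documents. The illustration rests on an assumed mean and SD and on all the removed patients scoring 6 in one group. It shows what the clause would allow, not what is expected. On those assumptions, several removals could move the uncontrolled mean by a good part of its CI half-width, while a single one would hardly matter. The clause should be rewritten before the tables are run, but the study is not invalidated by it.

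**What to change.** Rewrite SAP 3.1 as follows:
1. Complete the range and consistency review, with queries to sites, before closure and before any by-group table is produced.
2. After closure, set to missing only impossible values on a list written in advance: item score outside 1 to 6, TTR outside 0 to 100%, negative durations. Keep valid extreme values.
3. Delete interpolation.
4. Remove a patient only where the eligibility checks in SAP 4 are then not met. A flat ban on removal would be wrong, because it would retain patients whom SAP 4 excludes.
5. State that a VKA patient whose TTR is set to missing is not eligible and is not among the remaining patients whom SAP 5.1 assigns to the controlled group.
6. Show any affected primary table twice, from the unmodified closed data and after the change.

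The cost is SAP wording and at most a duplicate table. The edit checks that item 1 builds on are already planned.

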# REQUOL Study

## 4 POPULATION TO BE ANALYSED

The different populations included in the analysis are defined below:

- **Eligible patients** are defined as those who meet all the inclusion criteria and none of the exclusion criteria described in the protocol.

The CRF will contain information about the screening criteria in binary variable form (Yes/No) for each of the described items.

Several of these criteria can be verified with the data recorded in the CRF. The criteria to be verified to define the assessable population are described below:

### **SCREENING CRITERIA:**

- *The patient is willing to participate and grants his or her informed consent to participate in the study in writing.* The date of informed consent must be provided; it must be before or on the same date as the baseline visit.
- *The patient is at least 18 years old.* The patients' age must be 18 years or more (calculated from date of birth to the date of the baseline visit).
- *The patient has a diagnosis of NVAf.* The information regarding the NVAf-type variable must be completed.
- *The patient has been receiving the same anticoagulant treatment (VKA or DOAC) for at least 6 months and up to 2 years.* Time of treatment from the treatment start date to the date of the baseline visit must be at least 6 months and no greater than 2 years.
- *If he/she receives treatment with VKA, availability of TRT% in previous analytical records or sufficient INR determinations to calculate same.* If the patient is receiving treatment with VKA, the TRT% figure must be completed.

If there is a contradiction between the binary variables and the information shown in the CRF in question, the latter shall be assumed to be valid.

The number of unassessable patients in the study shall be provided, together with the reasons for their non-inclusion.

**The analyses will be performed with the eligible patients.**

# REQUOL Study

## 5 DESCRIPTIVE ANALYSIS.

### 5.1 Groups

The number of controlled vs uncontrolled patients shall be described.

The allocation of each patient to each group is performed automatically by the platform where the data are collected during the study and is performed at the time the VKA and TTR data are collected.

Patients receiving AVK and TTR (Rosendaal method) <65%, or TTR (direct method) <60% are assigned to the uncontrolled group. The rest of the patients are assigned to the controlled group.

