Study design:	
This observational multicenter and cross-sectional study will be conducted in Departments of Internal Medicine from approximately 50 centers in Spain
 
Approximately 500 patients seen in internal medicine are planned to be included in the study. To minimize selection bias at the patient level, consecutive patients from each site who meet entry criteria will be enrolled. The 3 participating autonomous communities planned are Madrid, Valencia and Andalucía. Patients should be included in a ratio 2:1, 2 patients controlled (VKA patients with a Time in Therapeutic range TTR ≥ 65% and all DOAC patients) per 1 patient uncontrolled (VKA patients with a TTR < 65%), due to the controlled patients comprise more treatments.
 
Control will be considered when INR values are between 2 and 3.
 
The design of the study impose an only visit to be performed that will
		

	
coincide with one of those performed by the patients as part of routine follow-up of their disease, without interfering with usual clinical practice of the investigator. A specific therapeutic strategy has already been assigned based on routine practice, and without interference with the physician's prescription habits. The observational nature of the study is ensured as no diagnostic or therapeutic intervention outside of routine clinical practice will be applied.

Population:	
Patients with non-valvular atrial fibrillation who are on the same anticoagulant therapy (VKA or DOAC) during at least 6 months and maximum 2 years will be included.
 
The patient will be considered included when he/she agrees to participate in the study by signing the informed consent.
 
The patient will be classified between controlled or uncontrolled group depending on the %TTR if VKA patients. If the %TTR collected from the analytical records was obtained by the Rosendaal method, VKA patients with a TTR < 65% will be allocated to the uncontrolled group and VKA patients with a TTR ≥ 65% will be allocated to the controlled group). If the %TTR was obtained by the direct method, the patient will be considered uncontrolled or controlled depending on whether the TTR value is < 60%. All DOAC patients will be allocated to the controlled group.

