### **Exclusion criteria:**

Patients will be excluded from participating in this study if 1 or more of the following criteria are met:

1. Current participation in any clinical trial of a drug or device
2. Contraindication to the use of DOAC or VKA as described in the Summary of Product Characteristics (SmPC).

A log of all patients included into the study (having given informed consent) will be maintained in the study file at the study site.

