### Collection of AEs

The study design is of non-interventional nature and the study is conducted within the conditions of the approved marketing authorisation. Sufficient data from controlled interventional trials are available to support the evidence on the safety and efficacy of the studied BI drug. For this reason the following AE collection and reporting requirements have been defined.

The following must be collected by the investigator in the (e)CRF from signing the informed consent onwards until the end of the study:

- all adverse drug reaction (ADRs) (serious and non-serious),
- all AEs with fatal outcome

All ADRs, including those persisting after study completion must be followed up until they are resolved, have been sufficiently characterized, or no further information can be obtained.

The investigator carefully assesses whether an AE constitutes an ADR using the information below.

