## **7 ADVERSE EVENT**

All the analyses in this section shall be performed for the controlled, uncontrolled and total populations.

The categorical variables to be described are: N and (%):

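### Adverse events of consented patients later found ineligible would be missing from the study report's adverse event counts and lists

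*SAP*

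**What the plan says.** **Who is analysed.** SAP section 4 defines one population, eligible patients: "those who meet all the inclusion criteria and none of the exclusion criteria described in the protocol". It closes with "The analyses will be performed with the eligible patients" and exempts no section. Protocol section 9.7 sets the same set: "The analysis population will consist of all eligible patients". Neither document defines a safety set.

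**How eligibility is settled.** SAP section 4 checks the five inclusion criteria against the recorded data. Where the two disagree, the recorded data override the site's Yes/No answers. For patients who fail, the SAP provides their number and the reasons, and nothing else.

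**What the adverse event section covers.** SAP section 7 opens with "All the analyses in this section shall be performed for the controlled, uncontrolled and total populations". It then asks for patient counts, a list of serious events and a list of Pradaxa-related events.

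**What is collected.** The protocol abstract (Population) sets the point of inclusion: "The patient will be considered included when he/she agrees to participate in the study by signing the informed consent". Protocol section 11.2 (Collection of AEs) requires all adverse drug reactions (ADRs) and all fatal adverse events (AEs) to be entered in the eCRF "from signing the informed consent onwards until the end of the study". No eligibility condition is attached.

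**The concern.** Events are collected from everyone who signs consent, but the report shows events only from those who pass the eligibility check. Ineligibility for a quality-of-life description is not a reason to leave a collected reaction out of the safety results.

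At stake is the completeness of the adverse event part of the report. Section 7 includes lists of individual events, where a single omission matters. The primary quality-of-life results are not affected.

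**Working it through.** The documents state no figure on this point that could be reproduced. The check is mainly a comparison of texts, followed by an illustration under stated assumptions.

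**Step 1. Does the eligible-only rule reach SAP section 7?** The closing rule of SAP section 4 has no exception. Section 7 names its populations in the same terms as SAP sections 5.2, 5.3 and 8.1 (demographics, atrial fibrillation history, quality of life). If 'total' means all eligible patients in those sections, nothing makes it wider in section 7. So the rule reaches it.

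**Step 2. Can a consented patient leave the eligible set?** Yes. Under the SAP section 4 check, this happens when, for example:
- the treatment start date gives less than 6 months or more than 2 years on treatment;
- the type of atrial fibrillation is blank;
- a VKA patient has no time in therapeutic range (TTR).

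Such a patient was included at consent and was already subject to ADR and fatal-event collection.

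**Step 3. Where would that patient's event still be seen?** This compares eCRF collection and expedited reporting (both protocol section 11.2) with SAP section 7.

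| Event in an unassessable patient | eCRF | NIS AE form to sponsor | SAP 7 output |
|---|---|---|---|
| ADR to Pradaxa | required | required (24 hours if serious, otherwise 7 days) | absent |
| Fatal AE, exposed to Pradaxa | required | required (24 hours) | absent |
| ADR to a VKA or another DOAC | required | not required | absent |
| Fatal AE, not exposed to Pradaxa | required | not required | absent |

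The first two rows reach the sponsor but not the report. The last two are in the database and in no planned output.

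**Step 4. Illustrative size.** The planned size is 330 + 170 = 500 (protocol section 9.5). The documents give neither an ineligible share *f* nor a rate *p* of patients with a collected event, so both are assumptions: *f* from 2% to 15%, *p* from 1% to 5%.

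- Unassessable patients: m = 500 × f
- Expected patients with events left out: m × p
- Chance that at least one is left out: 1 − (1 − p)^m

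| f | m | p | m × p | 1 − (1 − p)^m |
|---|---|---|---|---|
| 2% | 10 | 1% | 0.10 | 1 − 0.99^10 = 10% |
| 5% | 25 | 3% | 0.75 | 1 − 0.97^25 = 53% |
| 10% | 50 | 3% | 1.50 | 1 − 0.97^50 = 78% |
| 15% | 75 | 5% | 3.75 | 1 − 0.95^75 = 98% |

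The range is too wide to support a forecast. It shows only that the loss could be nil or a few patients.

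**The case against.** The strongest reply is that this is the protocol's own choice and that little depends on it. Protocol section 9.7 restricts the analysis population in the same way. The study is marked as not a PASS, and neither the objectives nor the outcomes include safety. Pradaxa events reach the sponsor whatever the analysis set, and the marketing authorisation holder reports to authorities (protocol section 11.3). There is one visit and no follow-up, only ADRs and fatal events are collected, and the exclusions are at least counted.

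Most of this stands, and it limits the point to a reporting gap. It does not close the gap, because section 7 is planned output and would be incomplete without saying so.

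A reader might infer more than the documents support:

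- *That the SAP departs from the protocol.* It does not; both use the eligible set.
- *That Pradaxa safety reports are lost.* They are not; the NIS AE form carries no eligibility condition.
- *That section 7 totals ought to match the NIS AE forms.* They would not under any analysis set, because the forms are required only for Pradaxa. Only the Pradaxa-related part could be expected to agree.
- *That the omission falls mainly on high-risk patients, because contraindication is an exclusion criterion.* No exclusion criterion is on the SAP's verification list, so a contraindication removes a patient only through the site's own answer. The documents do not show that the loss is non-random.
- *That a VKA patient without a TTR would be counted as controlled.* SAP section 5.1 sends the remaining patients to that group, but it also ties allocation to the moment the TTR is entered. The text leaves this open.

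**Conclusion.** The concern holds as a gap in the study report, shared by protocol section 9.7 and SAP section 4. As written, the events of consented but unassessable patients are absent from every count and list in SAP section 7. The Pradaxa-related list may be incomplete. ADRs to other anticoagulants, and fatal events in patients not exposed to Pradaxa, would appear in no planned output.

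The reading of the text is firm. The size is not: under the assumed rates, between 0.1 and 3.75 patients with events would be left out, and the true number is probably small. The point does not touch the primary or secondary objective, but it is worth correcting because the data are already collected.

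**What to change.** In SAP sections 4 and 7, state that adverse event counts and lists use all patients with valid signed consent, with unassessable patients flagged. Where the control group cannot be assigned, as for a VKA patient without a TTR, show the patient as 'not classified'. Keep the eligible set for SAP sections 5, 6 and 8. Patients without valid consent stay out. Record the change as a documented difference from protocol section 9.7.

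The cost is a sentence or two in the SAP, one flag or column in the section 7 tables, and the note on protocol 9.7. No new data are needed. The adverse event denominator will differ slightly from the quality-of-life denominator, which a footnote can explain.
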